6.5 Visit 2-Final visit (Week 2 +/- 1 day)

- a) Reassess cutaneous mastocytosis severity by (Global & Local) SCORMA Indexes; monitor vital signs
- b) Investigator Assessment of Global Improvement
- c) Quality of life assessment:SkinDex-16
- d) Review changes to medical history and current medications
- e) Review contraception (female patients of childbearing potential)
- f) Review adverse events
- g) Review compliance

- h) Repeat photographs
- i) Obtain levels of serum tryptase, urinary N-MH, LTE4, and 2,3 dinor 11β PGF2α
- j) Reconcile study formulation

6.6 Protocol Schedule of Events

	Week 0	Week
Study Activity	Screening &	2
	Baseline	
Visit Number	1	2
Allowable visit window in days		+/- 1
Review Eligibility	X	
Informed Consent	X	
Medical History	X	X
Dispense/Reconcile Medications	X	X
Review Changes to Medical History and Medications		X
Quality of Life Scale:SkinDex-16	X	X
SCORMA Index	X	X
Physical Exam	X	
Serum Tryptase, & urinary Mast cell mediators	X	X
Investigator Assessment of clinical response: initial and	X	X
subsequent; vital signs		
Photography	X	X
Adverse Event (Physician)		X
Adverse Event (Participant)		X
Review Dosing Compliance		X
Review Contraception	X	X
β-HCG ^a	X	
·		
a: Urine pregnancy test (women of childbearing potential)		

7 Statistical Plan

7.1 Sample Size determination

Due to the pilot nature of the study, no formal statistical power/sample size calculations are necessary. The sample size of 10 patients will be sufficient for this pilot study to obtain a preliminary estimate of treatment efficacy and to generate data that will be useful in the design of a larger study.

7.2 Statistical Methods

Continuous variables will be summarized using the sample mean, median, standard deviation, interquartile range, and range. Categorical variables will be summarized using number and percentage of patients.

7.2.1 Definition of response

Complete response:

Clinically significant SCORMA improvement in all 3 parameters of treated, involved skin: % skin involvement; activity or symptoms &/or

Improvement in all 3 SkinDex-16 domains (Emotions, symptoms, functioning) &/or Resolution of 75% of cutaneous lesions

Near Complete response:

Clinically significant SCORMA improvement in two of 3 parameters of treated, involved skin: % skin involvement; activity or symptoms and/or

Improvement in 2 SkinDex-16 domains (Emotions, symptoms, functioning) &/or Resolution of >50% of cutaneous lesions

Partial Response:

Clinically significant SCORMA improvement in one 3 parameters of treated, involved skin: % skin involvement; activity or symptoms and/or

Improvement in 1 SkinDex-16 domain (Emotions, symptoms, or functioning) &/or Resolution of >25% of cutaneous lesions

No response:

No significant SCORMA improvement in any of 3 parameters of treated, involved skin: % skin involvement; activity or symptoms and/or

Improvement in no SkinDex-16 domain (Emotions, symptoms, functioning) &/or Resolution of no cutaneous lesions.

*Additionally, for primary safety endpoints which will be scored as none, mild, moderate, or severe, the proportion of patients in each category at each follow-up time point will be estimated for each of the different safety endpoints. P-values of 0.05 or lower will be considered as statistically significant.

Handling of missing data

This is a prospective study and therefore we do not anticipate any missing data. In the event of any unexpected missing data, no attempt to impute this missing data will be made; missing data will simply be treated as missing in the statistical analysis.

Multiplicity

Since this is an exploratory pilot study, no adjustment for multiple testing is needed. P-value of 0.05 or lower will be considered as statistically significant.

Primary Hypothesis:

The study seeks to demonstrate the effectiveness and tolerability of a novel topical composition consisting of 3 components (diphenhydramine, aspirin and cromolyn sodium) in a neutral skin moisturizing cream (Vanicream) for the treatment of cutaneous lesions of mastocytosis. This will be determined by the proportion of participants who achieve complete or near-complete response utilizing the SCORMA Index, and SkinDex-16 QOL.

We will use the SCORMA index and SkinDex-16 as both continuous variables and categorical variables. Change in SCORMA and of SkinDex-16 from baseline to the 2week follow-up visit will be estimated using sample mean, median, standard deviation, interquartile range, and range. SCORMA and SkinDex-16 will be compared from baseline to the follow-up time point using a paired Wilcoxon signed rank test.

Interim Analysis

There will not be any interim analysis given the low risk profile of the study formulation.

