5.5 Masking/Blinding of Study

This is an open-label pilot investigation. Masking/blinding procedures are not applicable. Qualitative and quantitative evaluations of response to treatment will be recorded. Updated photographs will be included in participants' records time 0, and week 4.

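### Two limbs of the primary response definition (SCORMA and SkinDex-16) have no numeric cut-off, so the complete/near-complete rate is open to choice after unmasked scores are seen

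*Combined protocol and SAP*

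**What the plan says.** The combined protocol and SAP, section 7.2.1 (under Primary Hypothesis), states how effectiveness is judged: "This will be determined by the proportion of participants who achieve complete or near-complete response utilizing the SCORMA Index, and SkinDex-16 QOL".

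The same section builds each response category from up to three limbs:

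- **SCORMA.** Complete response: "Clinically significant SCORMA improvement in all 3 parameters of treated, involved skin". Near-complete: "Clinically significant SCORMA improvement in two of 3 parameters of treated, involved skin". Partial response needs one parameter. The no-response category changes the adjective: "No significant SCORMA improvement in any of 3 parameters of treated, involved skin". No amount is given in any of the four.
- **SkinDex-16 and lesion resolution.** Complete: "Improvement in all 3 SkinDex-16 domains (Emotions, symptoms, functioning) &/or Resolution of 75% of cutaneous lesions". Near-complete: "Improvement in 2 SkinDex-16 domains (Emotions, symptoms, functioning) &/or Resolution of >50% of cutaneous lesions". SkinDex-16 improvement has no amount. Lesion resolution does have figures: 75%, >50% and >25%.

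The SCORMA limb is tied to the others by the same and/or connector. The Global and Local response forms in the attachments repeat the SCORMA wording without a number, keep the lesion limb and leave SkinDex-16 out.

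Section 3.1 describes a non-randomised, open-label design. Section 5.5 adds: "Masking/blinding procedures are not applicable". The visit 2 list in section 6 includes an investigator assessment of improvement, and no masked or independent assessor is described. Section 7.1 sets 10 patients without a power or precision calculation.

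**The concern.** A responder rate can be reproduced only if two people given the same scores would classify each patient the same way. Here they could not. One could count any fall in a component, and another could ask for a halving. One could require all limbs, and another could accept any single limb. Nothing requires these choices to be made before week-2 scores are seen, or to be the same for every patient, and those who would make them know the treatment and the scores. With 10 patients, reclassifying one moves the rate by 10 percentage points.

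At stake is the proportion that section 7.2.1 says determines the primary hypothesis, and its value as the preliminary efficacy estimate that section 7.1 wants for designing a larger study.

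**Working it through.** The plan has no figure to reproduce: it gives no target rate, null rate, power or precision. The check is a reading of the definitions, then an illustration.

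**Reading.** Sections 3.2 and 7.2.1 and both response forms were searched for a number of points, grades or per cent attached to SCORMA improvement. There is none. Section 3.2 gives only the index formula, A/5 + 5B + 2C/5, and the item scales.

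**Illustration.** From the plan: three SCORMA parameters (taken as extent, intensity and symptoms), three SkinDex-16 domains, and responder status from at least two of three. Assumed: no true effect; independent components; chance *q* that one SCORMA component counts as improved; chance 0.5 that one SkinDex-16 domain counts (any fall); the two instruments independent; lesion limb left out.

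SCORMA limb: a = 3q²(1 − q) + q³. SkinDex-16 limb: s = 3(0.5)²(0.5) + (0.5)³ = 0.5. Combined: under *or*, 1 − (1 − a)(1 − s); under *and*, a × s.

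| q | a (SCORMA limb) | *or* | *and* |
|---|---|---|---|
| 0.1 | 0.027 + 0.001 = 2.8% | 1 − 0.972 × 0.5 = 51.4% | 1.4% |
| 0.2 | 0.096 + 0.008 = 10.4% | 55.2% | 5.2% |
| 0.3 | 0.189 + 0.027 = 21.6% | 60.8% | 10.8% |
| 0.5 | 0.375 + 0.125 = 50.0% | 75.0% | 25.0% |

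Moving q from 0.1 to 0.5 shifts the combined rate by 23.6 points under either rule (75.0 − 51.4, or 25.0 − 1.4). At any fixed q, changing *and* to *or* shifts it by a + s − 2as, which at s = 0.5 is 50 points. On these assumptions the unresolved connector matters more than the SCORMA cut-off.

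**Same scores, different bars.** A simulation drops independence within an instrument. Percentage changes are normal with mean 0, SD 25 and correlation 0.5 within each instrument (all assumed). The same simulated SCORMA changes are reclassified at each required fall, with SkinDex-16 still counted on any fall.

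| Required fall | SCORMA limb | *or* | *and* |
|---|---|---|---|
| any | 50.0% | 75.0% | 24.9% |
| 10% | 32.0% | 65.9% | 15.9% |
| 25% | 12.1% | 56.0% | 6.0% |
| 50% | 0.9% | 50.4% | 0.5% |

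The pattern holds. Adding the lesion limb could only raise the *or* figures and lower the *and* figures.

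**The case against.** Several points on the other side stand.

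- **SCORMA is not a gate for every category.** A reader might infer that every category depends on it. The and/or connector does not support that: read as *or*, a patient can be a complete or near-complete responder on SkinDex-16 or lesion resolution alone. SCORMA is required only if the connector is read as *and*.
- **The investigator does not control every input.** SkinDex-16 and the SCORMA symptom scales are subjective patient ratings, and the lesion limb has figures. Under *or*, the other limbs put a floor under the rate. That floor is weak protection, because the 50% used here comes from SkinDex-16 improvement also having no amount.
- **The upper end is generous.** Counting any fall (q = 0.5) stretches the phrase clinically significant, and intensity items scored 0 to 3 will often tie, so the null chance of a fall would be below one half. The lower rows still differ materially: the SCORMA limb goes from 2.8% to 21.6% between q = 0.1 and 0.3.
- **Other analyses survive.** The text after the Primary Hypothesis plans summaries of change in SCORMA and SkinDex-16 and a paired Wilcoxon signed rank test. These need no cut-off. Because component scores are recorded at both visits, a cut-off could also be applied later, but by then it would be chosen with the data in hand.
- **This is a 10-patient pilot.** Sampling error is already large: the exact 95% interval for 5/10 is 18.7% to 81.3%. That interval does not include the extra movement from choosing the definition.

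**Conclusion.** The point holds for the responder rate. Neither the SCORMA nor the SkinDex-16 limb has a numeric bar, the combination rule is ambiguous, and nothing fixes either before unmasked scores are seen. On the stated assumptions, the choice of SCORMA bar moves the SCORMA limb between 2.8% and 50% with no treatment effect. It moves the combined rate by about 24 points, within 51% to 75% under *or* or 1.4% to 25% under *and*. These are illustrations of sensitivity, not predictions. The values of q, the 0.5 per SkinDex-16 domain and the independence between instruments are not in the documents.

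A reader might go further and infer that the investigator can set the primary rate at almost any value, that the bar will be chosen patient by patient, or that all efficacy results are compromised. The documents do not support this. They show an opportunity and no intention; once one combination rule is adopted the illustrated range is bounded; and the Wilcoxon analysis is untouched. Nor do they state that the pilot's responder rate will be compared with a later study's. Section 7.1 speaks only of a preliminary estimate and of data for designing a larger study.

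**What to change.** Before any week-2 data are reviewed:

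1. Replace the undefined SCORMA phrase with a fixed numeric change from the patient's own baseline for each Local SCORMA parameter, keeping the three-, two- and one-of-three structure. One percentage-fall cut-off with a minimum absolute change would serve. Label it a convention: the documents support no particular value, and the lesion-resolution percentages are not offered there as thresholds for SCORMA. Use the same criterion in the no-response category.
2. State a minimum change for each SkinDex-16 domain. Without it, step 1 alone leaves the *or* rate at 50% or more on the assumptions above.
3. Replace the and/or connectors with one explicit combination rule, worded identically in section 7.2.1 and on the response forms, including whether SkinDex-16 is part of it.
4. Compute each patient's category from the recorded scores rather than by judgement, and report the response rate at one stricter and one looser cut-off.

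The cost is revised wording in section 7.2.1 and on the forms, with no added visits, measurements or patients. It does change the primary endpoint definition, so it belongs in an amendment, which section 11 sends to the IRB. The drawback is that the cut-offs are conventions; the two sensitivity cut-offs show how much depends on them.

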3.2 Primary Study Endpoints

Scorma Index[see below]

The proportion of participants who achieved complete resolution or near-complete clearing of cutaneous symptoms of treated, involved skin after 2 weeks' treatment will be evaluated using the SCORing MAstocytosis (SCORMA) index. SCORMA has been utilized to evaluate the severity of cutaneous mastocytosis and to correlate with serum tryptase levels. Repeated SCORMA determinations can "provide a rapid impression of changes in the clinical status" in mastocytosis (HeideR, van Doorn K, Mulder PG et al. Serum tryptase and SCORMA (SCORing MAstocytosis) index as disease severity parameters in childhood and adult cutaneous mastocytosis. Clinical and Experimental Dermatology 2008; 34: 462-468.)

The SCORMA index is calculated by the formula A/5 +5B +2C/5 where A=Extent of skin involvement,

B= Intensity (pigmentation/erythema + vesiculation + elevation + positive Darier's sign each rated 0[absent], 1[mild] 2[moderate] or 3[severe]).

C= subjective symptoms utilizing visual analog scale 1-10 of the following: provoking factor(s), flushing, diarrhea, pruritus, localized bone pain.

Since it will be impractical for patients to apply Skin Guard to the entire body surface area, and not all areas of the skin will be involved to the same extent, we will limit application to between 9% and 18% of the skin (see SCORMA figure). In this regard we will attempt, when possible, to utilize equally involved sides of the torso or extremities to facilitate evaluation of effectiveness. We will generate not only a "Global" SCORMA value, but in addition a SCORMA value for the treated, involved skin. The latter should give a more accurate estimation of the effectiveness on treated areas.

Quality of Life –SkinDex-16[see below]. Skindex-16, a validated measurement of the effects of skin diseases on patients' quality of life will be utilized to follow this parameter. SkinDex has been used and adapted for dermatologic research internationally (Chren M-M, The SkinDex instruments to measure the effects of skin disease on quality of life. Dermatology Clinics 2012; 30: 231-236).

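### Section 7.2.1 joins its response criteria by and/or with no order of precedence, so the primary response proportion is not determined

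*Combined protocol and SAP*

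**What the plan says.** Section 7.2.1 gives each category a SCORMA criterion for the treated skin (improvement in 3, 2, 1 or none of 3 parameters). It joins this by *&/or* (Complete) or *and/or* (the other three) to a SkinDex-16 criterion and a lesion criterion:

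- Complete: "Improvement in all 3 SkinDex-16 domains (Emotions, symptoms, functioning) &/or Resolution of 75% of cutaneous lesions"
- Near complete: "Improvement in 2 SkinDex-16 domains (Emotions, symptoms, functioning) &/or Resolution of >50% of cutaneous lesions"
- Partial: "Improvement in 1 SkinDex-16 domain (Emotions, symptoms, or functioning) &/or Resolution of >25% of cutaneous lesions"
- No response: "Improvement in no SkinDex-16 domain (Emotions, symptoms, functioning) &/or Resolution of no cutaneous lesions"

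The Primary Hypothesis paragraph in the same section says how effectiveness is judged: "This will be determined by the proportion of participants who achieve complete or near-complete response utilizing the SCORMA Index, and SkinDex-16 QOL".

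Section 3.2 describes the responder proportion as "complete resolution or near-complete clearing of cutaneous symptoms of treated, involved skin", evaluated by SCORMA. It lists SkinDex-16 as a separate entry, introduced as "Skindex-16, a validated measurement of the effects of skin diseases on" patients' quality of life.

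The Global and Local response forms in Section 15 repeat the and/or wording, leave SkinDex-16 out, and provide an assessment column with no rule for filling it.

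Section 7.1 expects the study to "obtain a preliminary estimate of treatment efficacy and to generate data that will be useful in the design of a larger study".

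**The concern.** A response definition should place every participant in exactly one category. This one does not, for three reasons.

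- The connector allows either *and* or *or*, and the two readings give very different results.
- No order of precedence is given. Under *or*, the highest and lowest categories can both apply to one person.
- The building blocks are open. No threshold makes a SCORMA improvement clinically significant, and no minimum SkinDex-16 change is given. Nothing says how a SCORMA-only form result combines with SkinDex-16.

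The complete or near-complete proportion is the stated basis for the primary hypothesis and would feed the design of a larger study. In an open-label study, leaving the rule open means it could be settled after outcomes are known.

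**Working it through.** The plan gives no response rate, benchmark or derived sample size, so there is no figure to reproduce. The check lists every outcome profile and classifies it under the 7.2.1 wording.

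**Inputs, from 7.2.1.** SCORMA parameters improved, *s* = 0–3. SkinDex-16 domains improved, *k* = 0–3. Lesion resolution in 5 bands: 0, >0–25%, >25–50%, >50–<75%, ≥75%. Total 4 × 4 × 5 = 80 profiles.

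**Conventions.** 75% is read as ≥75%. The >50% and >25% thresholds have no upper limit, as written. Counts of parameters and domains are taken either as exact (2 means 2) or as at-least (2 means 2 or 3). A responder is Complete or Near complete.

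**Read as *or*.**

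- Non-responders have *s* ≤ 1, *k* ≤ 1 and lesions ≤50%: 2 × 2 × 3 = 12. Responders: 80 − 12 = 68.
- Profiles that miss No response have *s* ≥ 1, *k* ≥ 1 and lesions >0: 3 × 3 × 4 = 36. Of these, 2 are non-responders (*s* = 1, *k* = 1, lesions >0–25% or >25–50%). Responders free of No response: 36 − 2 = 34. Responders that also meet No response: 68 − 34 = 34.
- Complete: 80 − (3 × 3 × 4) = 44. Complete without No response: 36 − (2 × 2 × 3) = 24. Both Complete and No response: 44 − 24 = 20.
- Profiles meeting more than one category, by direct count: 74 (exact) or 76 (at-least).

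**Read as *and*.**

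- Exact: Complete 1, Near complete 2, Partial 3, No response 1, so 7 are classified and 80 − 7 = 73 fit nothing. Responders: 1 + 2 = 3.
- At-least: Partial or better 3 × 3 × 3 = 27, plus 1 No response, so 80 − 28 = 52 fit nothing. Responders: 2 × 2 × 2 = 8.

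| Reading | Responder profiles of 80 |
|---|---|
| *Or*, highest category met | 68 |
| *Or*, No response overrides | 34 |
| *Or*, lowest category met | 4 exact, 0 at-least |
| *And* | 3 exact, 8 at-least |

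**SkinDex-16 in or out** (*or*, highest category). Responder status changes where *k* is 2 or 3, *s* ≤ 1 and lesions are ≤50%: 2 × 2 × 3 = 12 profiles.

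**The SCORMA-only forms** (4 × 5 = 20 profiles, *or*). Responders: 20 − (2 × 3) = 14. Of these, 4 also meet No response (2 with *s* ≥ 2 and no lesion resolved, 2 with *s* = 0 and lesions >50%). Two profiles are both Complete and No response.

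**Illustration on the rate scale.** Assume the three criteria are independent and each reaches near-complete or better with probability *q*. The responder rate is 1 − (1 − *q*)³ under *or* (highest category) and *q*³ under *and* (at-least).

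| *q* | *Or* | *And* |
|---|---|---|
| 0.2 | 48.8% | 0.8% |
| 0.3 | 65.7% | 2.7% |
| 0.5 | 87.5% | 12.5% |

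Positive correlation between the criteria would narrow the gap.

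**Size per participant.** 1/10 = 10 percentage points.

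**The case against.** The strongest reply is that the intent can be inferred. The categories run in descending order, and No response most naturally describes someone negative on everything. Assigning the highest category met then removes the contradiction. The clash between Complete and No response also needs the *or* reading: under *and*, no profile is in both.

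This is a reasonable guess at intent, but it is written nowhere and leaves *and* versus *or* open. Switching to *and* replaces the overlap with 52 to 73 unclassified profiles.

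Several limits stand:

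- The profiles are equally weighted and some are implausible, so the counts are not probabilities. The lowest-category reading is one that few analysts would adopt.
- Some counts depend on convention. With upper limits on the lesion bands and exact counts, the overlap becomes 72, the lowest-category responders 12, the unclassified 76 and the *and* responders 2. The figures 20, 34 and 68 do not change.
- This is an exploratory pilot, and no test or success threshold is attached to the proportion. The signed rank tests on SCORMA and SkinDex-16 do not use the categories.
- The proportion will be imprecise anyway: the exact 95% interval for 5 of 10 is 18.7% to 81.3%.
- Using SkinDex-16 both on its own and within the composite is not a contradiction in itself, since 7.2.1 says both scores are used as continuous and categorical variables. The gap is the missing rule for combining it with the SCORMA-only forms.

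None of this makes the proportion computable from the text. An imprecise estimate is acceptable in a pilot; one whose definition is unsettled is not.

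**Conclusion.** The concern holds. As written, 7.2.1 gives contradictory categories under *or* (20 of 80 profiles are both Complete and No response; 34 of 68 responder profiles also meet No response). Under *and* it gives no category for 52 to 73 of 80. Responder profiles range from 68 down to single figures, depending on choices the plan does not make.

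The counts rest on the stated lesion-band conventions and on equal weighting; they do not predict how many participants would be misclassified. The contradiction itself rests on the wording alone. It affects the complete or near-complete proportion, hence the primary hypothesis as stated, and not the continuous-score analyses. It must be fixed before data are reviewed.

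**What to change.** Replace the and/or connectors with one ordered rule for the treated area: assign the highest category met, and make No response require that every included criterion is negative. If *or* is meant and SkinDex-16 stays in:

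- **Complete:** 3 parameters, 3 domains, or ≥75% of lesions resolved.
- **Near complete:** otherwise 2 parameters, 2 domains, or >50%.
- **Partial:** otherwise 1 parameter, 1 domain, or >25%.
- **No response:** all others.

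This splits the 80 profiles 44/24/10/2. Without SkinDex-16, the 20 profiles split 8/6/4/2.

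The sponsor must decide and record:

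- Whether *or* is meant. If *and*, the 52 to 73 profiles that now fit nothing must be placed.
- Whether SkinDex-16 belongs in the composite, as in the hypothesis, or is reported as its own primary endpoint, as Section 3.2 lists it.
- The minimum SCORMA change and, if SkinDex-16 stays, the minimum domain change.
- Where lesion resolution of >0–25% goes. The rule above puts it in No response, which alters the current no-lesions wording. Putting it in Partial alters the >25% threshold and gives 44/24/11/1, or 8/6/5/1 without SkinDex-16. Responders are unchanged either way (68 of 80, or 14 of 20).

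Use the same wording in 3.2, 7.2.1, the hypothesis and both forms. Reporting the proportion with an exact 95% confidence interval would also help, though it is not needed to cure the defect.

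The cost is wording only, with no new data. Before minimum changes are applied, the ordered rule with SkinDex-16 equals the most lenient current reading (68 of 80). Applying minimum changes or dropping SkinDex-16 may lower the reported rate.

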1.1 Background

Condition to be studied

Mastocytosis is a rare disorder of clonal mast cell proliferation. There are several subclasses of systemic mastocytosis (SM) ranging from indolent disease to aggressive disease, mast cell leukemia and mast cell sarcoma. The major criterion for defining systemic disease is the presence of mast cell (MC) infiltration of organs (commonly assessed by tissue or bone marrow biopsy). Patients with SM may or may not have cutaneous involvement. Whereas in cutaneous mastocytosis (CM), MC infiltration is limited to the skin.

Why the investigational product may be beneficial

Topical treatment of symptoms resulting from cutaneous involvement by mastocytosis (pruritus, flushing, urticaria, angioedema) is mainly limited to topical lubricants, topical corticosteroids, and topical antihistamines, medications that have individually been available for decades. In our own experience, topical cromolyn sodium 0.25% (children), and 1% or 5% (adults) can also be effective for relief of dermal symptoms.

Excessive application of topical steroids can cause skin atrophy or delayed healing, while excessive absorption of topical antihistamines could lead to systemic side effects such as somnolence, dyskinetic symptoms, impairment of performance skills, anticholinergic symptoms and others.

The product to be used will not contain corticosteroids and will use a lower concentration of diphenhydramine (1% vs 2%) than is currently available in over the counter preparations. By combining 3 ingredients, diphenhydramine, cromolyn sodium and trolamine we will leverage the different effects of various classes of medications to block mast cell mediator release (cromolyn sodium), to block mediator (histamine) receptors (diphenhydramine) and to inhibit production of prostaglandin D2 by topical cyclooxygenase blockade (trolamine salicylate).

Pathophysiology relevant to potential study treatment action

Symptoms from mastocytosis result from accumulation of these cells as well as local and remote effects of MC mediators. Mast cells are dynamos for the production of mediators that in the skin can stimulate symptoms by their effects on blood vessel constriction, vasopermeability, and excitation of nerve endings causing itching, hiving, swelling and flushing. The synergistic effect of targeting 3 of the most prevalent (and measurable) mediators should have a beneficial effect on dermatologic symptoms and will allow a lower

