3.4 Primary Safety Endpoints

Minimal systemic absorption is expected with each of the active components. Safety endpoints to be measured at the initial and final visits and include Investigator and Participant observation of local skin tolerability including ratings of itching, swelling

stinging/ burning, and dryness on separate scales as none (0), mild (1), moderate (2), or severe (3).

4 Subject Selection Enrollment and Withdrawal

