4.4 Early Withdrawal of Subjects

4.4.1 When and How to Withdraw Subjects

Patients are free to withdraw at any time and for whatever reason. No data will be collected for withdrawn subjects and withdrawn subjects will not be replaced. There will be no follow-up for withdrawn subjects. Pre-specified reasons for discontinuing include, but are not limited to, the following:

- Patient request: Patient decided that he/she did not want to continue (for any reason).
- •Adverse Event: Patient experienced a related or unrelated event that would interfere with the study objectives/evaluation
- •Lost to Follow-up: Patient did not come in for a visit and could not be reached by phone
- Treatment Failure: If in the Principal Investigator's judgment, the patient's condition required another form of treatment
- •Noncompliance: Patient is not complying with the protocol requirements (i.e. visit schedule, dosing, regimen, etc.); a patient is to be withdrawn if he/she misses two consecutive visits
- •Other: Any other reason

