For this study, the study treatment follow-up period is defined as the last scheduled visit.

Preexisting condition

A preexisting condition is one that is present at the start of the study. A preexisting condition should be recorded as an adverse event if the frequency, intensity, or the character of the condition worsens during the study period.

General Physical Examination Findings

At screening, any clinically significant abnormality should be recorded as a preexisting condition. At the end of the study, any new clinically significant findings/abnormalities that meet the definition of an adverse event must also be recorded and documented as an adverse event.

Post-study Adverse Event

All unresolved adverse events are to be followed by the Principal Investigator and/or Investigators until the events are resolved, the subject is lost to follow-up, or the adverse event is otherwise explained. At the last scheduled visit, the Principal Investigator and/or Investigators should instruct each subject to report and any subsequent event(s) that the Participant, or the Participant's personal physician, believes might reasonably be related to participation in this study.

Abnormal Laboratory Values

A clinical laboratory abnormality that can reasonably be related to the administration of the study formulation should be documented as an adverse event.

Page 17 of 32

Hospitalization, Prolonged Hospitalization or Surgery

Hospitalization, prolonged hospitalization, or surgery is to be reported as an adverse event if it can reasonably be related to the administration of the study formulation.

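### The primary safety ratings are reported only as week-2 category proportions, which cannot show how many patients worsened from week 0

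*Combined protocol and SAP*

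**What the plan says.** Section 3.4 defines the primary safety endpoint as four local tolerability items, each graded none, mild, moderate or severe (0 to 3) by both investigator and participant: "Safety endpoints to be measured at the initial and final visits". The Primary Safety Endpoints Table in Section 15 accordingly has columns for weeks 0 and 2.

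The only analysis specific to these ratings is in the safety paragraph of Section 7.2.1: "the proportion of patients in each category at each follow-up time point will be estimated for each of the different safety endpoints". Sections 6.5 and 6.6 show a single follow-up visit, at week 2. The same paragraph sets a 0.05 significance threshold but names no test for the ratings.

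Two other statements bear on the analysis. Section 7.2 gives a general rule: "Categorical variables will be summarized using number and percentage of patients". The text under the primary hypothesis in Section 7.2.1 plans change from baseline for two instruments only: "SCORMA and SkinDex-16 will be compared from baseline to the follow-up time point using a paired Wilcoxon signed rank test".

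Separately, Section 8.1 says that a preexisting condition "should be recorded as an adverse event if the frequency, intensity, or the character of the condition worsens", and adverse events are reviewed at the week-2 visit.

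**The concern.** A tolerability rating is informative when it is read against the same patient's starting value. That matters here because Section 1.1 lists the skin symptoms of the disease as "pruritus, flushing, urticaria, angioedema", so itching and swelling can be present before any cream is applied. The population description in Section 1.1 also expects patients whose symptoms are bothersome despite treatment, although Section 4.1 does not make this an entry criterion. A week-2 grade of moderate itching may therefore be better than, the same as, or worse than at entry.

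Section 7.1 justifies the ten patients as enough "to generate data that will be useful in the design of a larger study". A per-patient worsening rate is one of the figures a larger study would want, and the planned summary does not produce it.

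Withdrawal adds to the problem. Section 4.4.1 lists adverse events among the reasons for stopping and states "No data will be collected for withdrawn subjects and withdrawn subjects will not be replaced". Patients who tolerated the cream worst may have no week-2 grade and drop out of the proportions.

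**Working it through.** The plan states no safety rate or power figure, so there is nothing of its own to reproduce. The question is what the planned summary can reveal about the number of patients who worsened.

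**Inputs from the documents:** 10 patients, one arm (Section 7.1); four grades per item (Section 3.4); one follow-up visit (Section 6.5). The documents give no baseline distribution, so every distribution below is an assumption.

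**Step 1: week-2 proportions alone.** Any patient graded above none at week 2 may or may not have been lower at week 0. The number worsened is therefore bounded only by 0 and the number graded above none. With week 2 at 2 none, 4 mild, 3 moderate and 1 severe, the range is 0 to 10 − 2 = 8. Ten patients can be spread over four grades in 286 ways, and only one of them, all graded none, fixes the count (at 0).

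**Step 2: week-0 proportions added, as Section 7.2 would allow.** Take the simple case where patients are graded either none or moderate, with k0 moderate at week 0 and k2 at week 2. If w patients go from none to moderate, then k2 − w remain moderate. This requires 0 ≤ k2 − w ≤ k0 and w ≤ 10 − k0, so

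max(0, k2 − k0) ≤ w ≤ min(k2, 10 − k0).

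With k0 = 6 and k2 = 4: max(0, −2) = 0 and min(4, 4) = 4. The percentage moderate falls from 60% to 40%, yet between 0 and 4 patients may have worsened. A linear-programming bound over the full 4 × 4 table gives the same range. If the 2/4/3/1 distribution of Step 1 is seen at both visits, the range is 0 to 6.

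**Step 3: the rates these counts imply (Clopper-Pearson, 95%).**

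| Worsened | Rate | Exact 95% CI |
|---|---|---|
| 0 of 10 | 0% | 0% to 30.8% |
| 4 of 10 | 40% | 12.2% to 73.8% |

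**Step 4: withdrawals.** Assume 2 of 10 have no week-2 grade and none of the other 8 worsened. The upper limit for 0 of 8 is 1 − 0.025^(1/8) = 36.9%. Counting both unrated patients as worsened gives 2/10 = 20% (2.5% to 55.6%).

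**The case against.** The strongest reply is that nothing is lost. Both ratings are to be taken and stored, so a shift table for ten patients can be made at any time, and the pilot is exploratory. That is true of the data, but the plan still commits the primary safety endpoint to a summary that does not answer the tolerability question. The week-0 rating is also less secure than it looks: it is not named in Sections 6.1, 6.5 or 6.6, where the adverse event rows are marked only at week 2.

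Second, worsening is captured elsewhere. Section 8.1 covers worsening of preexisting conditions, Section 8.2 requires all adverse events to be recorded, and SkinDex-16 and SCORMA include itching, with burning or stinging in SkinDex-16. This stands in part: worsening is not lost to the trial. But the adverse event rule is not tied to the 0 to 3 scale, and the two instruments are analysed as composites that do not cover swelling or dryness.

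Third, missing data are partly handled. Section 9.3 requires missing data to be explained, and Section 7.3 keeps every treated patient in the primary analysis. Neither supplies a week-2 grade for someone who left.

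Fourth, the example is extreme: four worsened means that all four symptom-free patients became moderate and all six moderate patients cleared. That is fair. The range shows what the percentages cannot exclude, not a likely result. It is also fair that the estimate will be imprecise with ten patients, and that a one-grade threshold is a choice the documents do not dictate.

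**Conclusion.** The concern holds. As written, the summary cannot give the number of patients who worsened on the primary safety scale, except in the trivial case where every patient is graded none at week 2. Adding week-0 percentages would not generally repair it. The size of the gap depends on a baseline that the documents do not give; in the assumed 6-of-10 to 4-of-10 example, the worsening rate is left anywhere from 0% to 40%. The confounding with disease symptoms is clearest for itching and swelling. This is a weakness in the endpoint's analysis, not a failure to monitor safety, and it is worth correcting because the remedy uses a baseline the trial already plans to collect.

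**What to change.** In Section 7.2.1, replace the safety sentence with the following: for each item and each rater, report a week-0 by week-2 shift table and the number and percent of patients with at least a one-grade worsening from week 0, with an exact 95% confidence interval. Beside each, report how many treated patients have no week-2 rating and the recorded reason for withdrawal.

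Name the tolerability rating in Section 6.1 (before the first application), in Section 6.5, and in both columns of Section 6.6. Remove the p-value threshold from the safety paragraph, since no test is planned for these ratings. State the limit plainly: in a single-arm study, worsening cannot be attributed to the cream rather than to a flare of the disease.

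The cost is analysis wording and a few schedule lines. The form already has both columns, and the reason for withdrawal must be recorded consistently. Four items by two raters gives 4 × 2 = 8 sparse tables in ten patients, so the main text can carry one line per item (number worsened, interval, number unrated) with the full tables in a listing.
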